2.2.3. Other and exploratory endpoints

- Pharmacokinetic:
 - $AUC_{0-7d, norm}$, $C_{max, norm}$, $t_{1/2, 0-24h}$, $t_{1/2, 0-7d}$, t_{max} , MRT, points terminal

3. Study design and study design rationale

3.1. Study design

This is a single-centre, open-label, randomized, parallel-group relative bioavailability study in healthy men. The study will be done in 2 parts, as follows:

- Part 1 – single oral doses of 5 mg emodepside will be tested:
 - Part 1a – the LSF (reference formulation) and 2 new IR-tablet formulations (test formulations) will be administered in the fasted state.
 - Part 1b – the 2 new IR-tablet formulations will be administered in the fed state (high-fat, high-calorie meal).
- Part 2 – single oral doses of 10 mg emodepside will be tested: depending on the results from Part 1, one or both IR-tablet formulations will be administered in the fasted state.

The treatments in each study part are summarised in Table 1.

Table 1. Planned treatments by dose, formulation and condition

Part	Treatment	Formulation, dose and condition	Number of subjects
Part 1a	A	5 mg emodepside LSF, fasted	12
	B	5 mg emodepside IR-tablet #406, fasted	12
	C	5 mg emodepside IR-tablet #416, fasted	12
Part 1b	D	5 mg emodepside IR-tablet #406, fed	12
	E	5 mg emodepside IR-tablet #416, fed	12
Part 2	F*	2 x 5 mg emodepside IR-tablet #406, fasted	12
	G*	2 x 5 mg emodepside IR-tablet #416, fasted	12

* one or both treatments may be tested, depending on results from Part 1

Up to 84 healthy volunteers will be enrolled, in up to 7 treatment arms made up of 12 subjects each.

The 36 subjects in Part 1a will be randomised to one of 3 treatments (A, B or C). The 24 subjects in Part 1b will be randomised to one of 2 treatments (D or E). Parts 1a and 1b may proceed in parallel, or may be done sequentially.

After at least 10 subjects have received each treatment in Part 1, and data up to 72 h after dosing are available, there will be a Dose Decision Meeting to determine which treatment(s) will be tested in Part 2 (see section 7.5).

In Part 2, either treatment F, G or both F and G will be tested. There will be 12 subjects enrolled for each treatment tested. If both treatments are tested, they will be done in parallel, and subjects will be randomised to one of the 2 treatments.

The study will be performed in a single site specialized in Phase 1 studies.

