1.5. Assessment and management of risk

The factors taken into account in the assessment of risk to subjects in this study are as follows:

- The planned single doses of emodepside have been administered to humans and were well tolerated. Based on the FIH single ascending dose clinical study, overall tolerability to emodepside has been acceptable up to 20 mg of LSF formulation. Post-dose visual disturbances were observed more frequently at 40 mg, and although these visual and nervous system disturbances were considered non-serious and mild in intensity, dose escalation was stopped at this dose level. All visual disturbances were transient in nature and resolved spontaneously within 24 h, and without treatment.
- Pre-clinical data suggests that plasma exposure following emodepside as IR-tablets is not higher than the one observed after LSF administration at the same dose.
- In Part 1 of this study, single doses of 5 mg emodepside will be administered in the fed and fasted states. Based on PK data from the FIH study, exposure to emodepside following administration of the IR-tablet in the fed state is likely to be similar to or lower than the IR-tablet administered in the fasted state. Therefore, it is acceptable to test the fed and fasted doses in parallel or sequentially in Part 1.
- Part 2 of this study, in which single doses of 10 mg emodepside will be tested, will proceed only if the PK, safety and tolerability after single doses of 5 mg emodepside in Part 1 are acceptable, and provided the Investigator and Sponsor's Medical Monitor agree that it is appropriate to give a higher dose. The total dose of emodepside for any subject will not exceed 10 mg.

2. Study Objectives and Endpoints

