2.1. Objectives

2.1.1. Primary Objective

- To investigate the pharmacokinetics, including relative bioavailability and food effect, of two new immediate release (IR)-tablet formulations of emodepside in comparison to the liquid service formulation (LSF) oral solution.

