3.4. Rationale of study design

The study will be performed in a randomized, open-label, parallel group design.

The open design of the trial has the important disadvantage that both investigator and subjects are aware that active treatment is being given, and there is no placebo. The possibility of bias must therefore be taken into account in the assessment of AEs in particular. However, the primary objective of the study is to compare the PK of emodepside after different formulations, which will be assessed using an objective test measured by an external laboratory. Relative bioavailability and food effect form part of the PK assessment. Most of the other assessments are also objective, either because they are measured by a laboratory or are measured using automated means (HR, BP, and ECG).

After a single dose, emodepside is rapidly absorbed and peak plasma concentrations occur within a few hours after dosing. There is a short half-life in the first 24 h

(distribution/elimination phase) followed by a long terminal elimination half-life ($t_{1/2}$ >500 h). Crossover designs are attractive because they can enhance the power of a trial to distinguish between treatments; that is because within-subject variability is generally less than between-subject variability. However, crossover designs are subject to carryover of effects from one treatment to the next, especially if the elimination half-life is long. Because of this, a parallel group design was chosen for this study and PK samples will be taken at the Follow-up Visit (168 h after dosing). Treatments in Part 1 will be randomized to reduce the likelihood of period or seasonal effects confounding the study assessments. Part 2 will also be randomized if both treatments are tested.

The study will be performed in healthy male Caucasian volunteers, in order to avoid ethnic and sex differences that may increase pharmacokinetic variability.

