7.1. Doses and treatment regimens

The study will be done in 2 parts. In Part 1, each subject will receive a single oral dose of 5 mg emodepside in the fasted state (Part 1a) or in the fed state (Part 1b). In Part 2, each subject will receive a single oral dose of 10 mg emodepside in the fasted state.

In Part 1, two new IR-tablet formulations of emodepside (#406 and #416) will be compared to LSF solution (concentration 1 mg/mL). In Part 2, one or both IR-tablet formulations from Part 1 will be tested.

Each subject will receive a single dose of emodepside. The treatments in each study part will be as follows.

- Part 1a:
 - Treatment A: 5 mg emodepside LSF, fasted
 - Treatment B: 5 mg emodepside IR-tablet #406, fasted
 - Treatment C: 5 mg emodepside IR-tablet #416, fasted
- Part 1b:

- Treatment D: 5 mg emodepside IR-tablet #406, fed
- Treatment E: 5 mg emodepside IR-tablet #416, fed
- Part 2:
 - Treatment F: 2 x 5 mg emodepside IR-tablet #406, fasted
 - Treatment G: 2 x 5 mg emodepside IR-tablet #416, fasted

In Part 1a, subjects will be randomized 1:1:1 to receive Treatment A, B or C. In Part 1b, subjects will be randomized 1:1 to receive Treatment D or E. Depending on the results from Part 1, all subjects in Part 2 may receive Treatment F, all subjects may receive Treatment G, or half of the subjects may receive each treatment. If one treatment is tested, 12 subjects will be allocated to that treatment. If both treatments are tested subjects will be randomized 1:1 to receive Treatment F or G. Enrolled subjects will be given a unique ID (subject number; Table 2) that will be recorded in the case report form (CRF), and will be retained throughout the study. This subject number will also appear on the study medication containers.

Table 2. Study treatment and subject numbers by study part

Part	Treatment	Number of subjects	Subject numbers
Part 1a	A, B or C	36 (12 per treatment)	1001–1036
Part 1b	D or E	24 (12 per treatment)	2001–2024
Part 2	F or G*	24 (12 per treatment)	3001–3024

* one or both treatments may be tested, depending on results from Part 1. If only one treatment is selected, the first 12 subject numbers will be used.

Replacements for withdrawn subjects will be given a number equal to that of the subject that they replaced plus 100 (e.g. Subject 1036 would be replaced by Subject 1136).

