15.2 Pharmacokinetic Parameters

The pharmacokinetic parameters will be listed and summarised by treatment.

To assess the relative bioavailability, analysis of variance (ANOVA) models will be fitted to the tablet (test) and solution (reference) data with the logarithm of the pharmacokinetic parameters $AUC_{0-7d}/Dose$ or $C_{max}/Dose$ as the dependent variable, and formulation as a fixed effect. The point estimates least squares (LS)-means and 90% confidence intervals for the ratios “B/A” and “C/A” will be calculated in Part 1a. In Part 2, “F/A” and/or “G/A” will be calculated. The acceptance range 80 – 125% will be applied for these assessments.

In part 1, to assess the effect of food, ANOVA models will be fitted to the data with the logarithm of the pharmacokinetic parameters $AUC_{0-7d}/Dose$ or $C_{max}/Dose$ as the dependent variable, and fed (test) or fasted (reference) as a fixed effect. The point estimates and 90% confidence intervals for the ratios “D/B” and “E/C” will be calculated. The acceptance range 80 – 125% will be applied for the assessment of a potential food effect.

To assess dose proportionality, for each tablet type, exploratory ANOVA models will be fitted to the relevant fasted data in Parts 1 and 2 with the logarithm of the pharmacokinetic parameters AUC_{0-7d} or C_{max} as the dependent variable and dose as a fixed effect. The ratios “F/B” and/or “G/C” will be calculated, with their 95% confidence interval.

16 References

1. International Conference on Harmonization, 1998. Statistical Principles for Clinical Trials - ICH Harmonised Tripartite Guideline. Guidance for Industry, E9, FDA federal register, Vol 63, 1998, p49583. Available at: <http://www.fda.gov/cder/guidance>.
2. International Conference on Harmonization, 1995. Structure and Content of Clinical Study Reports - ICH Harmonised Tripartite Guideline. Guidance for Industry, E3, FDA federal register, Vol 61, 1996, p37320. Available at: <http://www.fda.gov/cder/guidance>.
3. International Conference on Harmonisation, 2005. Clinical Evaluation of QT/QTc Interval Prolongation and Proarrhythmic Potential for Non-Antiarrhythmic Drugs. Concept paper, Guidance for Industry, E14, Center for Drug Evaluation and Research (CDER). Available at: <http://www.fda.gov/cder/guidance/6922fnl.htm>.
4. Julious, SA & Debarnot, CAM (2000) “Why are Pharmacokinetic Data Summarised by Arithmetic Means?”, Journal of Biopharmaceutical Statistics, 10 (1), p55-71

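### The food-effect contrasts D/B and E/C, part of the primary objective, are not randomised: fed and fasted arms come from separate randomisations that may run one after the other

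*Protocol*

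**What the plan says.** The primary objective (Protocol 2.1.1, SAP 4.1.1) is "To investigate the pharmacokinetics, including relative bioavailability and food effect, of two new immediate release (IR)-tablet formulations of emodepside" relative to the oral solution. Protocol 11.7 and SAP 15.2 estimate the food effect as D/B for tablet #406 and E/C for tablet #416, with 90% confidence intervals judged against 80–125%. The model is an ANOVA on log AUC0-7d/Dose or log Cmax/Dose, "and fed (test) or fasted (reference) as a fixed effect"; no other term is listed.

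Protocol 3.1 and 7.1 randomise the 36 men of Part 1a 1:1:1 to A, B or C, all fasted. Part 1b is a different set of 24 men, all fed: "In Part 1b, subjects will be randomized 1:1 to receive Treatment D or E". Table 2 gives the two parts separate number blocks, 1001–1036 and 2001–2024. Under Protocol 6, men join a cohort according to their availability and the trial dates.

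On timing, Protocol 3.1 and SAP 5 state that "Parts 1a and 1b may proceed in parallel, or may be done sequentially". The reason, in Protocol 1.5, is that fed exposure is expected to be no higher than fasted: "Therefore, it is acceptable to test the fed and fasted doses in parallel or sequentially in Part 1". Comparability is not discussed there. Protocol 3.4 makes a general claim for the design: "Treatments in Part 1 will be randomized to reduce the likelihood of period or seasonal effects confounding the study assessments".

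**The concern.** Randomisation supports comparisons between arms on the same list. Here that covers B/A, C/A, B against C, and D against E. It does not cover D/B or E/C, because each takes its numerator from one list and its denominator from the other. The protection against period and seasonal effects claimed in Protocol 3.4 therefore does not reach the food contrasts.

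The interval for D/B or E/C reflects sampling variation between subjects. It makes no allowance for a systematic difference between the two parts, such as a change in who is recruited, season, ward session or assay batch. Such a difference would be read as a food effect, or would hide one. Part 1 PK also informs which tablets go into Part 2 (Protocol 7.5).

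**Working it through.** **The plan's own figure.** 7 arms × 12 = 84, and 36 + 24 + 24 = 84, as stated. Protocol 11.1 and SAP 8.1 give no power calculation, so there is none to reproduce.

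**Can the analysis separate food from study part?** All of B and C are in Part 1a and all of D and E are in Part 1b. For either tablet, the fed/fasted indicator equals the part indicator, so a part or period term is collinear with food. If exposure in Part 1b differs from Part 1a by a factor k for reasons other than food, the expected ratio is (true food ratio) × k.

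**Inputs for the size of the problem**
- n = 12 per arm, so 22 degrees of freedom; t(0.95, 22) = 1.717.
- Between-subject CVs from the first-in-human study, solution, fasted (Protocol 3.4): 5 mg Cmax 16.8%, 5 mg AUClast 22.6%, 10 mg Cmax 26.8%. No CVs are given for the tablets or the fed state, and AUClast stands in for AUC0-7d.
- Shift between parts: not given in the documents, so a range of 2% to 15% is assumed.

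**Formulas**
- Log SD = √ln(1 + CV²); SE of the log ratio = log SD × √(2/12).
- 90% interval = ratio ×/÷ exp(1.717 × SE).
- Coverage = P(|T| < 1.717), where T is noncentral t with 22 df and noncentrality ln(1 + shift)/SE.

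For CV 22.6%: log SD = 0.2232; SE = 0.2232 × 0.4082 = 0.0911; interval factor = exp(1.717 × 0.0911) = 1.169. A 10% shift is ln(1.10)/0.0911 = 0.0953/0.0911 = 1.05 standard errors.

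**Coverage of the nominal 90% interval**

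| CV | 2% shift | 3% | 5% | 10% | 15% |
|---|---|---|---|---|---|
| 16.8% | 88.7% | 87.0% | 81.9% | 61.2% | 36.5% |
| 22.6% | 89.2% | 88.3% | 85.5% | 73.2% | 56.2% |
| 26.8% | 89.5% | 88.8% | 86.7% | 77.8% | 64.8% |

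**Effect on the 80–125% verdict.** Simulation, 200,000 runs per setting, 12 per arm, no true food effect. Entries are the chance that the 90% interval lies within 80–125%.

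| CV | k = 1 | 0.95 | 0.90 | 0.85 | 0.80 |
|---|---|---|---|---|---|
| 16.8% | 87% | 78% | 51% | 22% | 5% |
| 22.6% | 53% | 47% | 31% | 15% | 5% |

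The chance that the interval excludes 1 rises from 10% at k = 1 to about 45% (CV 16.8%) or 31% (CV 22.6%) at k = 0.90.

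**Masking.** With a true ratio of 0.80 and k = 1.11, the expected ratio is 0.80 × 1.11 = 0.89. The chance of meeting 80–125% rises from 5% to 44% (CV 16.8%) or 28% (CV 22.6%). With a true ratio of 0.67, the AUC effect reported for the solution in Protocol 1.4, and the same k, it stays below 1%.

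**The case against.** The case for leaving the design alone has four parts.

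- **A large shift is unlikely.** There is one site, one narrow set of entry criteria, standardised post-dose meals on Day 0, one bioanalytical laboratory and about six months overall. Nothing in the documents suggests that emodepside PK varies by season or session. A shift of 2–3% would do almost no harm, and the 37% coverage figure joins the largest assumed shift to the smallest CV. If tablet CVs were higher, the loss would be smaller: at an assumed CV of 35%, a 10% shift leaves 83%.
- **Imprecision matters more.** The study is called exploratory. Even with no shift and no food effect, the chance of meeting 80–125% is only 53% at CV 22.6%, and 29–35% at the 10 mg CVs. Part 2 is fasted whatever the food result.
- **A strong food effect would still show.**
- **Full aliasing with time arises only under sequential conduct,** and chance differences between subjects are already in the interval.

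All of this stands as a limit on the probable size of the bias. None of it makes the comparison randomised. Parallel conduct would largely remove the period component, but men would still enter a part by availability and dates. Low precision does not excuse an avoidable bias, particularly when the plan applies a fixed acceptance range to the result.

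**Conclusion.** The concern holds. D/B and E/C are non-randomised comparisons within the primary objective, the protection claimed in Protocol 3.4 does not extend to them, and the planned model cannot repair this. Under sequential conduct, food is completely confounded with period.

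The structural point rests on the text alone. The size depends on an assumed shift and on CVs from the fasted solution: negligible harm at 2–3%, coverage of 61–78% at 10%. The exposed region is a modest food effect near the 80–125% limits. The design should be corrected before dosing, because the data cannot be adjusted for it afterwards.

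**What to change.** Use one Part 1 randomisation list: the 60 subjects allocated 1:1:1:1:1 to A, B, C, D or E, run concurrently and blocked so that fed and fasted arms appear in each dosing session.

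- Remove the sequential option from Protocol 1.5 and 3.1 and from SAP 5.
- Replace the two randomisations in Protocol 3.1, 7.1 and SAP 5 with one, and merge the two Part 1 number blocks in Table 2.
- In Protocol 6, make clear that availability decides the dosing date and not whether a man is fed or fasted.
- Where meal and pre-dose instructions are tied to Part 1b (Protocol 4.3, the Section 5 footnote, Table 3, and the SAP 6 footnote), tie them to Treatments D and E.

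Arm sizes (60/5 = 12), doses, meals, contrasts and precision do not change: the interval factor stays at 1.124 for CV 16.8% and 1.169 for CV 22.6%. The cost is a new list, document edits, and serving the test breakfast to some men in a session while others fast. Protocol 1.5 already accepts parallel fed and fasted testing on exposure grounds.

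If one list is not workable, run Parts 1a and 1b in parallel with random assignment to part. Failing that, report D/B and E/C as non-randomised comparisons, show baseline comparability (body weight at least), and state that caveat beside the 80–125% result.

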3.2. Study duration and duration of subject participation

Each subject will attend a Screening visit within the 4 weeks before their dose of study medication (on Day 0).

Eligible subjects will be admitted to the ward on the afternoon of Day -1 (the day before dosing). They will remain on the ward until the morning of Day 3 (4 nights and 5 days in a row); during that time, they will receive a single oral dose of emodepside.

[figure not shown]
Safety, tolerability, and PK assessments will be done before and regularly after dosing. Each subject will undergo a full day of assessments (including PK) on the day of dosing (Day 0).

Subjects will be discharged from the study unit on Day 3, provided there are no medical objections. Subjects will attend the ward for outpatient (ambulatory) visit on Day 5 and a final Follow-up visit on Day 7, at 1 week after their dose of emodepside.

The study design is summarised schematically in Figure 1.

The study Schedule of assessments (Section 5) provides a detailed overview of all study procedures, which are further discussed in Section 8 (Study Assessments).

Figure 1 – Overall study design

3.3. Definition of the end of trial

The end of the trial is defined as the final Follow-up visit by the last subject (or final contact with the subject, if that is later).

If the trial is terminated early, the trial ends when the Sponsor notifies the Investigator in writing that the trial has finished, or when the last subject attends the final Follow-up visit, whichever is later.

3.4. Rationale of study design

The study will be performed in a randomized, open-label, parallel group design.

The open design of the trial has the important disadvantage that both investigator and subjects are aware that active treatment is being given, and there is no placebo. The possibility of bias must therefore be taken into account in the assessment of AEs in particular. However, the primary objective of the study is to compare the PK of emodepside after different formulations, which will be assessed using an objective test measured by an external laboratory. Relative bioavailability and food effect form part of the PK assessment. Most of the other assessments are also objective, either because they are measured by a laboratory or are measured using automated means (HR, BP, and ECG).

After a single dose, emodepside is rapidly absorbed and peak plasma concentrations occur within a few hours after dosing. There is a short half-life in the first 24 h

(distribution/elimination phase) followed by a long terminal elimination half-life ($t_{1/2}$ >500 h). Crossover designs are attractive because they can enhance the power of a trial to distinguish between treatments; that is because within-subject variability is generally less than between-subject variability. However, crossover designs are subject to carryover of effects from one treatment to the next, especially if the elimination half-life is long. Because of this, a parallel group design was chosen for this study and PK samples will be taken at the Follow-up Visit (168 h after dosing). Treatments in Part 1 will be randomized to reduce the likelihood of period or seasonal effects confounding the study assessments. Part 2 will also be randomized if both treatments are tested.

The study will be performed in healthy male Caucasian volunteers, in order to avoid ethnic and sex differences that may increase pharmacokinetic variability.

In the FIH study, single doses of 5 and 10 mg emodepside, administered as LSF oral solution in the fasted state, were safe and well tolerated. Since those doses are likely to fall within the dose range tested in later phase studies, and have previously been well tolerated in healthy volunteers, they have been selected for this relative bioavailability study. It is anticipated that emodepside exposure following IR-tablets (in both fasted and fed states) will be no higher than exposure following the same dose of LSF oral solution. Anticipated exposures for each formulation tested in this study are provided below.

Following a single dose of 5 mg emodepside, administered as LSF oral solution in the FIH study, mean \pm SD (CV%) C_{max} was 93.2 ± 15.7 ng/mL (16.8%) and AUC_{last} was 1736.2 ± 392.5 ng \cdot h/mL (22.6%). Exposures in Part 1 of this study are likely to be similar to, or lower than, these values.

Following a single dose of 10 mg emodepside, administered as LSF oral solution in the FIH study, mean \pm SD (CV%) C_{max} was 178.6 ± 47.9 ng/mL (26.8%) and AUC_{last} was 3165.2 ± 817.2 ng \cdot h/mL (25.8%). Exposures in Part 2 of this study are likely to be similar to, or lower than, these values.

The highest single dose which has been shown to be well tolerated is 20 mg LSF oral solution, which resulted in mean \pm SD (CV%) C_{max} of 315.7 ± 87.6 ng/mL (27.7%) and AUC_{last} of 7617.0 ± 1467.7 ng \cdot h/mL (19.3%). Even if exposures in Parts 1 and 2 are higher than anticipated, they are unlikely to exceed these values.

Therefore, the proposed doses to be tested in this study are considered acceptable.

4. Selection of Subjects

The following eligibility criteria were designed to select subjects for whom the protocol treatment is considered appropriate. All relevant medical and non-medical conditions should be taken into consideration when deciding whether this protocol is suitable for a particular subject. Eligibility criteria may not be waived by the Investigator. Any questions regarding a subject's eligibility should be discussed with DNDI Medical Monitor before the subject's enrolment.

